9.5.4 Other Assessments

Blood samples will be obtained from subjects in both cohorts for pharmacokinetic assessment of concomitant anti-epilepsy drugs. Blood samples will be drawn at Visits 1, 2, 3, 4, 5, 7, 8, 9 and 10.

Blood samples for pharmacokinetic assessment of ganaxolone from both cohorts will be drawn at Visits 4, 5, 7, 8, 9 and 10.

The time of the blood sample collection, and the time of the most recent dose prior to the blood sample collection will be recorded. Samples of blood will be centrifuged to obtain plasma, which will be stored frozen (-20°C) until analysis.

Both sets of pharmacokinetic samples will be drawn and retained for assessment on an as-needed basis, for example, to evaluate compliance or drug-drug interactions. Procedures will be put in place to ensure maintenance of the blind should analysis occur during double-blind treatment. For the purposes of this protocol, ganaxolone and concomitant AED PK assessments will not be considered as safety assessments.

9.5.5 Schedule of Study Procedures

Refer to [Appendix I](#) for tabular Schedule of Study Procedures.

The visit window for Phase 1 Double-blind Randomization Visit 2 is +3 days, however, subjects must have a minimum of 28 days of prospective baseline seizure charting. Visit windows are ± 3 days for Phase 1 Double-blind (Visits 3-5) and Visit 6 of Phase 2 Open-label and ± 7 days Phase 2 Open-label (Visits 7- Post taper Safety Follow up), respectively.

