De-escalation Period: The study drug will be decreased in increments of 450mg/d in 4-day intervals over 12 days for 1800 mg. Decreases from doses less than 1800 mg will be adjusted accordingly (See Table 1 & 2). The subject will return for final post-taper safety assessment visit.

Details of the dosing regimen are provided in the table below.

Table 1. Dosing Schedule for Cohort 1 Double-blind Phase, Open-Label Phase, and De-Escalation Period

Cohort 1, Phase 1- Double-blind				
Visit	Study Day	Dose (mg)/day	200 mg cap/day or matching placebo	225 mg cap/day or matching placebo
Titration to 1200 mg/d (Visit 2)	1	400	2	0
	2	400	2	0
	3	800	4	0
	4	800	4	0
	5	1200	6	0
	6	1200	6	0
	7	1200	6	0
1200 mg/d Maintenance (Visit 3)	8- 35	1200	6	0
Step Titration to 1800 mg (Visit 4)	36	1800	0	8
1800 mg/d Maintenance	37-63	1800	0	8

Cohort 1, Phase 2- Open-label					
DB Transition to Open-Label					
Visit	Study Day	Dose (mg)/day		Bottle A 225 mg or PBO cap/day	Bottle B 225 mg or PBO cap/day
				GNX: 225 mg	GNX: 225 mg
		GNX/GNX	PBO/PBO	PBO: 225 mg	PBO: PBO
Visit 5	64	1800	900	4	4
	65	1800	900	4	4
	66	1800	1350	6	2
	67	1800	1350	6	2
	68	1800	1350	6	2
	69	1800	1800	8	0
	70	1800	1800	8	0

Cohort 1, Phase 2- Open-label			
All Subjects			
Visit	Study Day	Dose (mg)/day	225 mg cap/day
1800 mg/d Maintenance Visit 6	71	1800	8
OL Flex Dosing Visit 6-10	72-427	1800 or MTD	8
Cohort 1, De-Escalation Study Completion or Early Termination			
Visit	Study Day	Dose (mg)/day	225 mg cap/day
Visit10 / Taper Visit/	Last full dose 427	1800	8
	428	1350	6
	429	1350	6
	430	1350	6
	431	1350	6
	432	900	4
	433	900	4
	434	900	4
	435	900	4
	436	450	2
	437	450	2
	438	450	2
	439	450	2
	440	0	0
	441	0	0

Table 2. Dosing Schedule for Cohort 2 Double-blind Phase, Open-Label Phase, and De-Escalation Period

Cohort 2, Phase 1- Double-blind			
Visit	Study Day	Dose (mg)/day	225 mg cap/day or matching placebo
Titration to 1800 mg/d (Visit 2)	1	450	2
	2	450	2
	3	450	2
	4	900	4
	5	900	4
	6	900	4
	7	1350	6
	8	1350	6
	9	1350	6
	10	1350	6
	11	1800	8
	12	1800	8
	13	1800	8
	14	1800	8
1800 mg/d Maintenance (Visit 3)	15-56	1800	8
1800 mg/d Maintenance (Visit 4)	57-98	1800	8

Cohort 2, Phase 2- Open-Label					
DB Transition to Open-Label					
Visit	Study Day	Dose (mg)/day		Bottle A 225 mg or PBO cap/day	Bottle B 225 mg or PBO cap/day
		GNX/GNX	PBO/PBO	GNX: 225 mg	GNX: 225 mg
				PBO: 225 mg	PBO: PBO
Visit 5	99	1800	450	2	6
	100	1800	450	2	6
	101	1800	450	2	6
	102	1800	900	4	4
	103	1800	900	4	4
	104	1800	900	4	4

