	105	1800	1350	6	2
	106	1800	1350	6	2
	107	1800	1350	6	2
	108	1800	1350	6	2
	109	1800	1800	8	0
	110	1800	1800	8	0
	111	1800	1800	8	0
	112	1800	1800	8	0

Cohort 2, Phase 2- Open-Label			
All Subjects			
Visit	Study Day	Dose (mg)/day	225 mg cap/day
1800 mg/d Maintenance Visit 6	113	1800	8
OL Flex Dosing Visit 6-10	114-477	1800 or MTD	8
Cohort 2, De-Escalation Study Completion or Early Termination			
Visit	Study Day	Dose (mg)/day	225 mg cap/day
Visit10 / Taper Visit/	Last full dose 478	1800	8
	479	1350	6
	480	1350	6
	481	1350	6
	482	1350	6
	483	900	4
	484	900	4
	485	900	4
	486	900	4
	487	450	2
	488	450	2
	489	450	2
	490	450	2
	491	0	0
	492	0	0

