9.5.3 Safety Assessments

Planned safety assessments include:

Neurological and physical examinations

Clinical laboratory tests

12-lead ECG

Vital signs including temperature, blood pressure, pulse rate, respiration rate, height, weight and BMI

Columbia Suicide Severity Rating Scale (C-SSRS)

AE monitoring: frequency, severity, duration, causality, outcome

Clinical labs, vitals and ECG measurements may be repeated if needed to corroborate or refute abnormal findings. Both the original and replicate assessments should be recorded in the eCRF.

See [Appendix 1](#) Schedule of Events for timing of Safety Assessments.

Adverse events will be presented for these time periods for Cohorts 1 & 2: ganaxolone vs placebo Titration + Maintenance (Cohort 1: Weeks 1-9, Cohort 2: Weeks 1-14), 1200

mg/d vs placebo (Cohort 1: Weeks 2-5), and 1800 mg/d vs placebo (Cohort 2: Weeks 6-9) for the safety population; open-label (Cohort 1: Weeks 10-61, Cohort 2: 15-66). In addition, tolerability of ganaxolone during the up-titration phases of the study will be compared between the two cohorts. AEs with onset during the titration phase in Cohort 2 will be compared to AEs with onset during the weeks 1-5 in Cohort 1 (1 week titration + 4 week treatment with 1200 mg/day). In addition, in Cohort 2, AEs with onset during the titration phase will be compared to AEs with onset during the maintenance phase. AEs that emerge during the de-escalation period will be tabulated to investigate whether discontinuation of ganaxolone is associated with withdrawal symptoms. Secondary safety outcome measures include those listed below.

Secondary Safety Parameters for Cohorts 1 & 2	Cohort 1		Cohort 2		Combine Cohorts 1 & 2	
	DB Phase	OL Phase	DB Phase	OL Phase	DB Phase	OL Phase
Number of subjects at each dose	X	X	X	X		X
The frequency and proportion of subjects with AEs	X	X	X	X		X
Severity of AEs	X	X	X	X		X
AEs leading to DC	X	X	X	X		X
Incidence of subjects with early DC	X	X	X	X		X
Change from baseline in vital signs (blood pressure, respiration rate and heart rate), body weight and ECG	X	X	X	X		X
Change in clinical hematology and chemistry parameters	X	X	X	X		X
Assessment of suicidality via the Columbia Suicide Severity Rating Scale (C-SSRS)	X	X	X	X		X

Additional assessments may be conducted as considered appropriate.

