9.5.5.14 Visit 10 Pre-Taper/ET Visit (Cohort 1: Week 61; Cohort 2: Week 66)

Concomitant AEDs reviewed; physical and neurological examinations performed; vital signs taken; ECG performed; blood samples drawn for hematology, chemistry, and study medication and concomitant AED levels; urine sample obtained for urinalysis and pregnancy test for WCBP; Columbia Suicide Scale assessed; AEs assessed; subject calendar reviewed; Clinician Global Impression of Improvement and Patient Global Impression of Improvement assessed; study medication compliance assessed; study medication dispensed.

9.5.5.15 Visit 11 Post-Taper Safety Follow-up Visit (Cohort 1: Week 63; Cohort 2: Week 68)

Concomitant AEDs reviewed; physical and neurological follow-up examinations performed; vital signs taken; urine sample obtained for pregnancy test for WCBP;

Columbia Suicide Scale assessed; AEs assessed; subject calendar reviewed; study medication compliance assessed.

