Adverse events will be summarized by treatment group and overall for each cohort and phase separately for subjects in the Safety Population. In Cohort 1 tables, AE's will be summarized by treatment, dose level, and overall for subjects in the Safety Population, adverse events of subjects pooled in Cohort 1 and Cohort 2 for each treatment phase will be summarized. The following AE tables will be generated:

- An overall summary of the number and percentage of subjects reporting AEs, serious SAEs, treatment-related AEs, AEs leading to treatment discontinuation and AEs leading to death
- AEs overall and by system organ class and preferred term
- AEs by maximum severity, overall and by system organ class and preferred term
- AEs by relationship to study treatment, overall and by system organ class and preferred term
- AEs with onset (or worsening) during titration + 1200 mg/day dose (weeks 1 to 5) and 1800 mg/d (weeks 6 to 9) by preferred term in Cohort 1 DB phase
- AEs with onset (or worsening) during titration phase and maintenance phase by preferred term in Cohort 2 DB phase
- AEs with onset (or worsening) during the de-escalation phase (time interval between Pre-Taper/Early Termination visit and Post-Taper Safety Follow Up visit) by preferred term in Cohort 1 and 2 OL phase

All AEs, SAEs, AEs leading to drug discontinuation and AEs leading to death will be listed.

Missing date will be imputed followed table describes how missing date information will be handled:

Partial Missing Start or Stop Date	Imputed Start Date	Imputed Stop Date
Missing month and day, and the year is present	January 1 of that year or first dose date if the year is the same as the year of first dose date	December 31 of that year
Missing day, but year and month are present	First day of that month or first dose date if the year and month are the same as the year and month of first dose date	Last day of that month
Missing month, but year and day are present	Missing month imputed as January	Missing month imputed as December

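### The ±7 day window for the post-taper safety visit overlaps the taper, so the de-escalation AE interval that ends at that visit can close before the last dose

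*Protocol*

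**What the plan says.** **Window.** Protocol 9.5.5 gives all later open-label visits one generic allowance, ± "7 days Phase 2 Open-label (Visits 7- Post taper Safety Follow up". It sets no separate limit on the early side for the last visit.

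**Visits.** Protocol 9.5.5.14 and 9.5.5.15 list "Visit 10 Pre-Taper/ET Visit (Cohort 1: Week 61; Cohort 2: Week 66" and "Visit 11 Post-Taper Safety Follow-up Visit (Cohort 1: Week 63; Cohort 2: Week 68".

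**Taper.** Protocol 9.4.5 states: "The study drug will be decreased in increments of 450mg/d in 4-day intervals over 12 days for 1800 mg". Table 1 (Cohort 1) has "Last full dose 427", taper doses on days 428-439 and 0 mg on days 440-441. Table 2 (Cohort 2) has "Last full dose 478", taper doses on days 479-490 and 0 mg on days 491-492. Tapers from lower doses are to be adjusted accordingly.

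**Intended order.** Protocol 9.3.4.2 (early termination), 9.4.5, 9.5 and 9.5.2 all place the final safety visit after de-escalation or at its end.

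**Analysis.** Protocol 9.5.3 says that AEs emerging during de-escalation are tabulated "to investigate whether discontinuation of ganaxolone is associated with withdrawal symptoms". SAP 9.3 defines that table as "AEs with onset (or worsening) during the de-escalation phase (time interval between Pre-Taper/Early Termination visit and Post-Taper Safety Follow Up visit".

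**The concern.** A visit can be within its permitted window and still take place during the taper it is supposed to follow. The SAP closes the de-escalation interval at that visit rather than at a time defined by the last dose. An early visit therefore removes the remaining taper days and all drug-free time from the interval, while the subject stays in the denominator. A new event on the last taper doses, or after them, would then be missing from the table built to answer the withdrawal question, and its incidence would be biased downward.

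**Working it through.** **Inputs.** Visit weeks are from Protocol 9.5.5.14 and 9.5.5.15, doses by day from Tables 1 and 2 in 9.4.5, and the ±7 days from 9.5.5. Study day = week × 7.

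**Reproducing the plan's figures.**
- Taper from 1800 mg/d: 3 steps (1350, 900, 450 mg/d) × 4 days = 12 days, as stated.
- Cohort 1: Week 61 × 7 = day 427, which matches Table 1. Week 63 × 7 = day 441, the last day in Table 1.
- Cohort 2: Week 66 × 7 = day 462 and Week 68 × 7 = day 476. Table 2 has the last full dose on day 478, which is 478 − 462 = 16 days later than Week 66. Its flexible-dosing row runs over days 114-477, that is 477 − 114 + 1 = 364 days or 52 weeks, whereas Protocol 9.1 allots 50 weeks.

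**Window against taper, from 1800 mg/d.** Last taper dose = last full dose + 12. Window = nominal Visit 11 day ± 7, which is 15 days.

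| Reading | Last full dose | Last taper dose | Nominal Visit 11 | Window | Dosing days in window |
|---|---|---|---|---|---|
| Cohort 1, Table 1 with Week 63 | 427 | 439 | 441 | 434-448 | 6 of 15 |
| Cohort 2, Table 2 alone (schedule ends day 492) | 478 | 490 | 492 | 485-499 | 6 of 15 |
| Cohort 2, Weeks 66 and 68 alone | 462 | 474 | 476 | 469-483 | 6 of 15 |
| Cohort 2, Table 2 doses with Week 68 | 478 | 490 | 476 | 469-483 | 15 of 15 |

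**Drug-free time, Cohort 1.**
- On schedule: 441 − 439 = 2 days.
- Latest permitted day: 448 − 439 = 9 days.
- Earliest permitted day (434): none. Table 1 has 900 mg/d on that day and five more taper days after it (435-439).

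**Lower doses.** Protocol 9.4.5 allows open-label doses down to 900 mg/d. Assuming the same 450 mg steps every 4 days:
- From 1350 mg/d, the last taper dose is day 427 + 8 = 435, so 2 of 15 window days are dosing days.
- From 900 mg/d, it is day 427 + 4 = 431, so 0 of 15.

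**Late Visit 10.** Visit 10 has the same ±7 days, and the documents do not say what Visit 11 is counted from.
- If it is counted from the study week (an assumption) and Visit 10 is *s* days late, the last taper dose is day 439 + *s*. The subject is on drug at the nominal day 441 when 439 + *s* ≥ 441, that is when *s* is 2 or more.
- If it is counted from the actual Visit 10 plus 14 days, the 6 of 15 is unchanged whatever the timing of Visit 10.

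**SAP windows.** The midpoint rule in SAP 6.4 does not help. The midpoint of Weeks 61 and 63 is (427 + 441) / 2 = day 434, the same lower edge.

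**The case against.** The strongest reply is that four sections fix the order: the taper comes first and the visit follows. On that reading, a visit on day 434 would breach the protocol even though it is within the window, and the defect is only a generic window without a lower limit. This stands as a description of intent. It also confirms the conflict, because a site scheduling by 9.5.5 would be in window and out of order.

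Some stronger readings are tempting, and the documents do not support them:

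- **That 40% of subjects are affected.** Six of 15 is a share of calendar days, and only for tapers from 1800 mg/d. Nothing in the documents shows how often visits will be early.
- **That Visit 11 is fixed to the nominal week.** No section says so. The synopsis and Protocol 9.1 place the final assessment two weeks after the open-label phase, which can be read as running from the actual end of treatment. Extreme cases, such as Visits 10 and 11 on the same day, depend on that unstated anchor and contradict the stated order.
- **That a subject seen early is counted as having no withdrawal event.** The SAP table counts every onset or worsening from Visit 10 up to the visit. Only later events can be lost.
- **That safety follow-up stops at Visit 11.** SAEs are reportable to 30 days after the last dose (SAP 9.3), and AEs unresolved at discontinuation are followed to resolution (Protocol 9.3.4.2). SAP 9.3 limits TEAEs to those before the end of study but does not define that as Visit 11. Part of Protocol 10.5.3 was not available for this review, so it cannot be inferred that non-serious AEs go uncollected afterwards.
- **That the last C-SSRS, pregnancy test or neurological examination must be off drug.** No text requires it.

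**Conclusion.** The inconsistency is real. For a taper from 1800 mg/d, 6 of the 15 permitted days for the post-taper visit are dosing days, against four sections that place the visit after the taper. With lower starting doses the overlap shrinks to 2 of 15 or to none, assuming the same taper steps. Cohort 2 adds a separate conflict: Table 2 and the visit weeks cannot both hold, and read together they put the whole Week 68 window on dosing days.

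The statistical consequence is possible truncation, with downward bias, of one descriptive safety table, mainly for new non-serious AEs. Its size cannot be estimated, because it depends on how many visits are early and on the unstated anchor. Even an on-time visit in Cohort 1 gives only 2 drug-free days in the interval. No efficacy endpoint or hypothesis test is touched. Severity is minor to moderate.

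**What to change.** - **Protocol.** Reconcile the 9.5.5 window and the Visit 10 and Visit 11 weeks with Tables 1 and 2 and with 9.3.4.2, 9.4.5, 9.5 and 9.5.2, so that an in-window visit cannot precede the end of the taper. State what Visit 11 is counted from, including for early terminators, to whom Weeks 63 and 68 cannot apply. Resolve the Cohort 2 day numbering at the same time. How these are settled is for the sponsor; no taper, dose or visit rule is proposed here.
- **SAP 9.3.** Define the de-escalation AE interval consistently with the reconciled end of dosing, and report with the table the number of drug-free days observed per subject. Extending the interval to the 30-day SAE period would not serve instead, since it would add mainly SAEs rather than the non-serious symptoms in question.

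The cost is a short clarification in 9.5.5, a footnote in Appendix 1, corrected day or week numbers for Cohort 2, and a line or two in SAP 9.3. The one drawback is less freedom to bring the last visit forward.

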9.5.5.1 Visit 1 (Screening Visit)

Written informed consent (signed informed consent form) obtained; demographics and medical history obtained; inclusion/exclusion criteria reviewed; seizure identification review and diagnostic review form submission; concomitant AEDs reviewed; physical and neurological examinations performed; vital signs taken; ECG performed; blood samples drawn for hematology, chemistry, and concomitant AED levels; urine sample

obtained for urinalysis and drug screen; qualitative serum pregnancy test for WCBP; Columbia Suicide Scale assessed; retrospective seizure diary collected and reviewed; subject calendar reviewed.

9.5.5.2 Visit 2 (Randomization; Week 0)

Approval of seizure identification and diagnostic review form required.

Inclusion/exclusion criteria reviewed; concomitant AEDs reviewed; physical and neurological follow-up examinations performed; vital signs taken; blood samples drawn for hematology, chemistry, and concomitant AED levels; urine sample obtained for urinalysis and pregnancy test for WCBP; Columbia Suicide Scale assessed; AEs assessed; subject calendar reviewed; randomization; study medication dispensed.

9.5.5.3 Visit 3 (Up-Titration; Cohort 1: Week 1; Cohort 2: Week 2)

Concomitant AEDs reviewed; physical and neurological examinations performed; vital signs taken; ECG performed 2-3 hours after dosing; blood samples drawn for hematology, chemistry, and concomitant AED levels; urine sample obtained for urinalysis and pregnancy test for WCBP; Columbia Suicide Scale assessed; AEs assessed; subject calendar reviewed; study medication compliance assessed; study medication dispensed.

9.5.5.4 Telephone Follow Up (Cohort 2: Week 5)

AEs assessed; concomitant AEDs and medications reviewed. Subject queried regarding any planned or unplanned changes in dose regimen.

9.5.5.5 Visit 4 (Evaluation; Cohort 1: Week 5; Cohort 2: Week 8)

Concomitant AEDs reviewed; physical and neurological follow-up examinations performed; vital signs taken; blood samples drawn for hematology, chemistry, and study medication and concomitant AED levels; urine sample obtained for urinalysis and pregnancy test for WCBP; Columbia Suicide Scale assessed; AEs assessed; subject calendar reviewed; Clinician Global Impression of Improvement and Patient Global Impression of Improvement assessed; study medication compliance assessed; study medication dispensed.

9.5.5.6 Telephone Follow Up (Cohort 2: Week 11)

AEs assessed; concomitant AEDs and medications reviewed. Subject queried regarding any planned or unplanned changes in dose regimen.

9.5.5.7 Visit 5 (Final DB Evaluation; Cohort 1: Week 9; Cohort 2: Week 14)

Concomitant AEDs reviewed; physical and neurological examinations performed; vital signs taken; ECG performed 2-3 hours after dosing; blood samples drawn for hematology, chemistry, and study medication and concomitant AED levels; urine sample obtained for urinalysis and pregnancy test for WCBP; Columbia Suicide Scale assessed; AEs assessed; subject calendar reviewed; Clinician Global Impression of Improvement and Patient Global Impression of Improvement assessed; study medication compliance assessed; study medication dispensed.

9.5.5.8 Visit 6 (DB Conversion; Cohort 1: Week 10; Cohort 2: Week 16)

Concomitant AEDs reviewed; physical and neurological follow-up examinations performed; vital signs taken; blood samples drawn for hematology, chemistry; urine sample obtained for urinalysis and pregnancy test for WCBP; Columbia Suicide Scale assessed; AEs assessed; subject calendar reviewed; study medication compliance assessed; study medication dispensed.

9.5.5.9 Visit 7 (Cohort 1: Week 14; Cohort 2: Week 20)

Concomitant AEDs reviewed; physical and neurological examinations performed; vital signs taken; ECG performed; blood samples drawn for hematology, chemistry, and study medication and concomitant AED levels; urine sample obtained for urinalysis and pregnancy test for WCBP; Columbia Suicide Scale assessed; AEs assessed; subject calendar reviewed; study medication compliance assessed; study medication dispensed.

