9.3 Selection of study population

9.3.1 Number of Subjects

Approximately 525 subjects will be screened to randomize approximately 46 subjects into Cohort 1 and approximately 359 subjects into Cohort 2 at a 1:1 ratio of ganaxolone to placebo, assuming a screen-failure rate of 15%. It is estimated that approximately 320 subjects will complete the 14-week double-blind phase of Cohort 2, which assumes approximately 10% discontinuation rate.

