9.3.4 Removal of Subjects from the Study

9.3.4.1 Criteria for Withdrawal

All subjects reserve the right to withdraw from the clinical study at any time, as stated in the informed consent form (ICF). The Investigator may discontinue subjects from the clinical study for any of the following reasons:

1. Post-treatment QTc interval >500 msec or uncorrected QT interval >600 msec; for subjects with bundle branch block, post-treatment QTc >530 msec based on average QTc value of triplicate ECGs. A subject with a post-treatment increase in QTc of >60 msec from Baseline must also be withdrawn.
 - a. If the initial electrocardiogram (ECG) indicates a QTc interval outside of these limits, then 2 additional ECGs should be collected and the average QTc value of these 3 ECGs will be used. If the average values of the triplicate ECGs exceed the stated limits, the subject must be withdrawn.
2. Subject is found to have entered the clinical investigation in violation of the protocol;

3. Subject requires the use of an unacceptable or contraindicated concomitant medication;
4. Use of benzodiazepines as rescue for innumerable seizure clusters more than two times during 9 or 14-week DB phase, or more than once in a 28-day period must be discontinued;
5. Use of benzodiazepines as rescue for innumerable seizure clusters more once in a 28-day period during the Open-Label Phase, Investigator should consider discontinuation;
6. Subject's condition changes after entering the clinical investigation so that the subject no longer meets the inclusion criteria or develops any of the exclusion criteria;
7. Subject is noncompliant with procedures set forth in the protocol in an ongoing or repeated manner;
8. Subject experiences an adverse event (AE) that warrants withdrawal from the clinical investigation;
9. It is the Investigator's opinion that it is not in the subject's best interest to continue in the study;
10. Any subject who exhibits any of the following will be immediately withdrawn from the clinical investigation:
 - a. Clinically significant worsening of seizures as judged by Investigator or subject such that treatment outside of the protocol is assumed to be in the subject's best interest.
 - b. Two episodes of generalized tonic-clonic seizures (GTCS) if not present at baseline.
 - c. Status epilepticus at any time during the clinical investigation.

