9.4.5 Study Dosing and Dosage Adjustments

Double-blind Phase:

Cohort 1: The study drug dose will be titrated from 400 mg/day to 1200 mg/day in divided doses BID by the end of Week 1 and maintained to Week 5. Dosage will be increased to 1800 mg/day Week 6 and maintained through Week 9 (Table 1).

Cohort 2: The study drug dose will be titrated from 450 mg/day to 1800 mg/day in divided doses BID by the end of Week 2 and maintained through Week 14 (Table 2).

Both titration schedules are consistent with acceptable starting doses and MTDs from previous ganaxolone studies.

Open-Label Phase: Following the completion of the double-blind (DB) phase in either cohort, subjects randomized to placebo will transition to ganaxolone while subjects randomized to ganaxolone will stay on 1800 mg/d. Cohort 1 placebo subjects will begin the 1-week dose titration to 1800 mg/d after completing their Visit 5. Subjects will receive ganaxolone 900 mg/d in divided doses BID for 2 days and step up to 1350 mg for 3 days and then increase to 1800 mg in divided doses BID for 2 days until their Visit 6 (Table 1). Titration for Cohort 2 placebo subjects will mirror the DB phase. Subjects will begin the 2-week dose titration to 1800 mg/d after completing their Visit 5. Subjects will start with 450 mg/d in divided doses BID for 3 days, 900 mg/d in divided doses BID for 3 days, 1350 mg/d in divided doses BID for 4 days, and 1800 mg/d in divided doses BID for 4 days until their Visit 6 (Table 2). At Visit 6, all subjects in both cohorts will be evaluated for tolerability and the investigator will make the determination to maintain the subject on 1800 mg/d or adjust their dose. If the patient experiences any tolerability issues during the transition to OL, such as sedation or dizziness, changes to the titration schedule (e.g., conducting the titration over 3 weeks vs. 2 weeks) may be approved after discussion with the medical monitor. Subjects may be maintained on the MTD of ganaxolone that provides adequate seizure control that is not less than 900 mg/d and not more than 1800 mg/d. Doses may be adjusted upward or downward in 225 mg/d increments every 3 days to reach an optimal dose level over the duration of the 52-week OL phase. Dose adjustments should be made with the investigator's agreement. Frequency of dosing changes may not be less than 3 days unless required for safety.

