6.2 Key Definitions

Calculation of Baseline:

For the primary efficacy endpoint(s):

For subjects enrolled under and prior to Amendment 2, baseline will be calculated based upon a combination of 4 weeks of prospective recording in a daily seizure calendar contiguous with 4 weeks of retrospective seizure history (seizure diary) which will be collected after obtaining informed consent. Acceptable retrospective daily seizure data include a diary record of the frequency and type of seizures by day, subjects without acceptable retrospective daily seizure data will not be randomized. After completing the 4-week prospective baseline period, eligible subjects are to be randomized to receive either ganaxolone or placebo.

For subjects enrolled under Amendment 3, baseline will be calculated based upon the 8 weeks prospective recording in a daily seizure calendar, which will be collected after obtaining informed consent.

For subjects still in the study at time of the primary analysis, last dose date will be considered the date of the most recent DB study visit in the database for that subject.

For safety endpoints, non-missing value of last assessment before first dose will be set as baseline value for both Cohort 1 and Cohort 2.

See Tables 1 and 2 in the protocol for details of the dosing regimen for each cohort/phase.

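### Subjects who switch from placebo have no scheduled ECG at peak ganaxolone level, because the open-label ECGs carry no timing relative to dose

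*Protocol*

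**What the plan says.** **Double-blind phase.** Protocol 9.5.5.3 (Visit 3) and 9.5.5.7 (Visit 5) both require "ECG performed 2-3 hours after dosing". Footnote 2 of both double-blind schedules in Appendix 1 describes this as the study drug's Tmax.

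**Open-label phase.** Protocol 9.5.5.9 (Visit 7) lists "vital signs taken; ECG performed; blood samples drawn for hematology, chemistry, and study medication and concomitant AED levels", and 9.5.5.14 (Visit 10, also the early-termination visit) uses the same words. Section 9.5.5.8 (Visit 6, the end of the switch titration) lists no ECG. In both open-label schedules the ECG row shows a plain mark at Visits 7 and 10. Footnote 2 there concerns the telephone calls, and no footnote mentions Tmax.

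**The switch.** Protocol 9.4.5: "subjects randomized to placebo will transition to ganaxolone while subjects randomized to ganaxolone will stay on 1800 mg/d". The switch titration starts once Visit 5 is complete.

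**QTc criteria.** Protocol 9.3.4.1 item 1 sets absolute limits and adds: "A subject with a post-treatment increase in QTc of >60 msec from Baseline must also be withdrawn". SAP 9.6 repeats these criteria. Neither text restricts them to a phase or an arm, and item 5 of the same protocol list names the open-label phase.

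**Baseline.** For safety endpoints SAP 6.2 says that the "non-missing value of last assessment before first dose will be set as baseline value for both Cohort 1 and Cohort 2".

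**The concern.** The protocol ties every scheduled on-treatment ECG in the double-blind phase to peak drug level. It drops that timing, without comment, at the point where the placebo arm first receives drug. A switcher's QTc is then compared with the withdrawal limits at whatever time after dosing the visit happens to fall. A recording made before the morning dose or late in the dosing interval could miss a peak value that meets a limit.

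A second, smaller effect is on interpretation. Open-label ECG change from baseline is a listed safety outcome (Protocol 9.5.3). For switchers it would be computed from recordings at mixed times after dose, against a screening ECG that precedes the whole placebo period.

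**Working it through.** **Step 1. Which scheduled ECGs fall on ganaxolone, and which are timed** (Protocol 9.5.5.1 to 9.5.5.15 read against Appendix 1):

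| Visit | ECG | Timing stated | Ganaxolone arm | Placebo arm |
|---|---|---|---|---|
| 1 (screening) | yes | none | no drug | no drug |
| 3 | yes | 2–3 h post-dose | ganaxolone | placebo |
| 5 | yes | 2–3 h post-dose | ganaxolone | placebo |
| 6 | no | – | ganaxolone | ganaxolone |
| 7 | yes | none | ganaxolone | ganaxolone |
| 10 / early termination | yes | none | ganaxolone | ganaxolone |

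The other visits have no scheduled ECG. Peak-timed ECGs on ganaxolone are therefore 2 per ganaxolone-arm subject and 0 per switcher. Every open-label subject has 2 untimed ones.

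**Step 2. How many switchers.** Inputs are all from Protocol 9.3.1. The numbers to be randomised are "approximately 46 subjects into Cohort 1 and approximately 359 subjects into Cohort 2". Allocation is equal between the arms. About 320 Cohort 2 subjects are expected to finish the double-blind phase, a figure "which assumes approximately 10% discontinuation rate".

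- Check of the plan's own figure: 359 × 0.90 = 323.1, against the stated 320. The 356 in SAP 3.4 gives 356 × 0.90 = 320.4. The stated figure is reproduced.
- Randomised to placebo: (46 + 359) / 2 = 202.5, about 202 of 405.
- Cohort 2 placebo completers: 320 / 2 = 160.
- Cohort 1 placebo: 46 / 2 = 23. The documents give no Cohort 1 dropout rate. Assuming 0 to 10%, 20.7 to 23 reach the switch.
- Expected switchers: 160 + 20.7 = 180.7 to 160 + 23 = 183, or about 181 to 183.

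**Step 3. When the untimed ECGs fall.** In Cohort 2 the first ganaxolone dose for placebo subjects is on day 99 (Table 2). Visit 7 is Week 20, day 140, so the first on-drug ECG is 140 − 99 = 41 days later, before the ±7-day visit window. The next is at Week 66, which is 66 − 20 = 46 weeks after that.

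**Step 4. Baseline for switchers.** Visit 2 has no scheduled ECG. The last scheduled ECG before the first dose of study drug is therefore the screening one, unless it was repeated at baseline for medical need (Appendix 1, footnote 4). Visit 5 is the last scheduled ECG before ganaxolone, but it is not the reference for change.

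**The case against.** The strongest reply is that this is a consistent choice. Visit text and all four schedules agree with one another, and footnote 2 states a timing without arguing for it. Peak QTc is measured where it can best be interpreted, in the ganaxolone arm with concurrent placebo. Both timed Cohort 2 ECGs and the Cohort 1 Visit 5 ECG fall at 1800 mg/d, and open-label dosing may not exceed that. Protocol section 7 reports no clinically significant ECG findings in a study up to 2000 mg/d and no such trends across the programme.

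Most of this stands, and it rules out one tempting reading: that the trial lacks peak-level QTc evidence. It does not answer for the individual switcher, to whom the withdrawal criteria apply. Background AEDs may be adjusted in the open-label phase (inclusion criterion 6), and carbamazepine and phenytoin, which 9.4.11 calls CYP3A4 inducers, are permitted. Double-blind peak conditions therefore need not match a given subject's open-label conditions.

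There is partial mitigation. At Visits 7 and 10 the times of the blood sample and the most recent dose are recorded (9.5.4), and the seizure calendar asks for the time of the last dose. Time after dose could be approximated if the ECG clock time were captured, but the documents do not say that it is. Abnormal ECGs may be repeated (9.5.3), but a repeat prompted by an abnormal finding cannot recover a peak that was never recorded. An untimed ECG may also fall at two to three hours by chance.

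On baseline, a reader might infer that the Visit 5 ECG goes unused. It does not: ECGs are summarised by visit (Protocol 9.7.7). It is only not the reference for change. For a placebo subject it is also a drug-free recording, and keeping the pre-randomisation baseline across phases is conventional. That is a reason to add a Visit 5 comparison, not to replace the baseline.

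**Conclusion.** The point holds in a limited form. About 181 to 183 expected switchers have no scheduled Tmax-timed ECG on ganaxolone, while QTc criteria without limit of phase or arm apply to them. The consequence is weaker individual monitoring and harder-to-read open-label QTc change in this group.

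The count assumes equal discontinuation in the two arms, 0 to 10% dropout in Cohort 1, and entry of all placebo completers into the open-label phase; fewer will reach Visit 7. A reader might use the 202 randomised to placebo instead, but that includes subjects who leave before receiving any ganaxolone. Nor does the 12-month safety objective rest on ECGs alone: adverse events, laboratory tests, vital signs, examinations and the C-SSRS also serve it. The documents give no basis for estimating how often a QTc limit would be missed, so none is claimed.

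Section 9.3.4.1 introduces the QTc item as something the investigator may act on and then words it as mandatory. The point does not depend on which reading applies. This is an inexpensive improvement, not a threat to the trial's conclusions.

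**What to change.** **Protocol 9.5.5.9, 9.5.5.14 and Appendix 1.** Reconcile the open-label visit text and schedules with the double-blind ECG footnote by applying the existing post-dose timing to the ECGs already scheduled at Visits 7 and 10, where the subject is still dosing. Visit 10 is also the early-termination visit, and some subjects will already be off drug; for them, record the time since last dose instead. Record the ECG clock time and the last-dose time on the ECG form in all cases.

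**SAP 9.6.** For placebo-to-ganaxolone subjects, add a summary of open-label QTc change from Visit 5 (the last scheduled ECG before ganaxolone), alongside change from the original baseline.

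**Cost.** Open-label Visits 7 and 10 must be booked around the dose, as Visits 3 and 5 already are, and there are two time fields and one extra table. No ECG is added, and no QTc limit or withdrawal rule changes.
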